**ABBREVIATIONS AND DEFINITIONS OF TERMS**
**List of Abbreviations**

ABBREVIATION	DEFINITION
AESI	Adverse Event of Special Interest
ALT	Alanine Aminotransferase
AST	Aspartate Aminotransferase
cccDNA	Covalently Closed Circular DNA
ChAdOx1	Chimpanzee Adenovirus Oxford 1
CHB	Chronic Hepatitis B Virus
CRF	Case Report Form
DMC	Data Monitoring Committee
DNA	Deoxyribonucleic Acid
eCRF	Electronic Case Report Form
ELISPOT	Enzyme-linked Immunospot
eTMF	Electronic Trial Master File
EU	European Union
FDA	Food and Drug Administration
GCP	Good Clinical Practice
GM	Genetically Modified
GMO	Genetically Modified Organism
HBcrAg	Hepatitis B Core-related Antigen
HBeAg	Hepatitis B e-Antigen
HBpgRNA	Hepatitis B Pregenomic RNA
HBsAb	Hepatitis B Surface Antibody
HBsAg	Hepatitis B Surface Antigen
HBV	Hepatitis B Virus
HCC	Hepatocellular Carcinoma
HCV	Hepatitis C Virus
HDV	Hepatitis D Virus
HIV	Human Immunodeficiency Virus
ICH	International Council on Harmonisation of Technical Requirements for Registration of Pharmaceuticals for Human Use
IEC	Independent Ethics Committee
IFN	Interferon
INR	International Normalised Ratio
IRB	Institutional Review Board
LFTs	Liver Function Tests
MedDRA	Medical Dictionary for Regulatory Activities
MERS	Middle East Respiratory Syndrome
MVA	Modified Vaccinia Virus Ankara
NA	Nucleotide Analogue
PBMC	Peripheral Blood Mononuclear Cell
PD-1	Programmed Cell Death Protein 1
PDL-1	Programmed Death-ligand 1
pfu	Plaque Forming Units
PT	Prothrombin Time

ABBREVIATION	DEFINITION
RNA	Ribonucleic Acid
SAE	Serious Adverse Event
SAS	Statistical Analysis Software
SI	Standard International
SMC	Safety Monitoring Committee
SUSAR	Suspected Unexpected Serious Adverse Reaction
TB	Tuberculosis
TEAE	Treatment Emergent Adverse Event
ULN	Upper Limit of Normal
vp	Viral Particles

## 1 BACKGROUND

### 1.1 Disease Review

Hepatitis B virus (HBV) is a complex, small deoxyribonucleic acid (DNA) virus that goes through a ribonucleic acid (RNA) intermediate life cycle requiring reverse transcription. After transmission through infected blood, contaminated body fluids or through perinatal transfer, the virus infects the liver and can then either integrate into the hepatocyte genome or can exist as a stable chromosomal closed circular DNA. Once infection takes place, HBV infection results in chronic liver disease in 5-10% of infected adults, whereas the rate for perinatal transmission is the opposite, with greater than 90% of infected neonates progressing to chronic disease [1]. After a chronic HBV (CHB) infection is established, the rate of natural clearance is minimal. Such CHB infection frequently progresses to necrotic inflammation and ongoing liver damage, which may lead to cirrhosis and hepatocellular carcinoma (HCC) [1].

### 1.2 Treatment Review

Highly effective prophylactic vaccines were implemented in the early 1980's; however, these vaccines are ineffective once infection is established [2]. Despite the wide use of prophylactic vaccines, there are an estimated 240 million CHB carriers and over 686,000 related deaths per year worldwide [3].

Two classes of antiviral therapies have been approved and recommended for treatment of hepatitis B: interferons (IFNs) and nucleotide analogues (NAs). The use of IFN results in higher rates of hepatitis B e-antigen (HBeAg) and hepatitis B surface antigen (HBsAg) loss compared to NAs.

Pegylated IFN administered for up to 52 weeks results in HBsAg loss in 3-7% of patients compared to 0-3% HBsAg loss after the same duration of NA therapy. Response to IFN is also more durable, and HBsAg loss may occur after cessation of treatment, while virological relapse is frequent after cessation of NA. However, IFN is less effective at suppressing viral replication compared to NAs, requires parenteral administration, is associated with significant side effects, and is contraindicated in patients with decompensated cirrhosis or severe exacerbations of hepatitis and those with autoimmune or psychiatric illnesses.

Nucleotide analogues are administered orally and have negligible adverse effects. The recommended first-line NAs, entecavir and tenofovir (tenofovir alafenamide fumarate or tenofovir disoproxil fumarate; hereafter referred to as tenofovir), have low risk of drug resistance; but the requirement for indefinite therapy increases the cost and the risk of non-adherence. [4]

Various combinations of IFN and NA have been evaluated, but most studies have not shown an added benefit compared to monotherapy [5,6,7]. A recent study showed that combination of pegylated IFN and tenofovir increased the rate of HBsAg loss to 9.1% at Week 72, but the benefit was mainly observed with those infected with HBV genotype A [8].

Many research programs are ongoing to develop new treatment concepts that focus on the clearance of HBsAg in a significant proportion of patients, with the principal aims of: 1) stopping treatment with no risk of virological relapse and no risk of liver disease progression and, 2) to further decrease the risk of HCC. Several potential target mechanisms for immune modulation to restore HBV specific immune responses in conjunction with profound inhibition of HBV replication and HBsAg production to attain immunological control are being evaluated [3].

The immune clearance of CHB is likely to depend on the use of modalities that induce effective CD8+ T cells [9,10]. For over two decades vaccination strategies to induce these CD8+ T cells to counter such infections as tuberculosis (TB), human immunodeficiency virus (HIV) and malaria have been investigated [11,12,13]. One platform approach that has induced remarkably high levels of T cells in man has been to use a non-replicating adenovirus "prime" followed by a heterologous viral vector "boost" utilising a non-replicating pox virus (modified vaccinia virus Ankara [MVA]) [14,15,16]. Non-replicating chimpanzee adenoviruses are often used rather than human adenoviruses, as there is minimal prior immunity to the vector itself [17,18]. The combination of chimpanzee adenoviruses (used in thousands of participants) plus MVA (administered to over 130,000 people) has been shown to induce large immune responses in man in malaria, TB, HIV, influenza, hepatitis C virus (HCV) and respiratory syncytial virus [13,16,19-22]. The chimpanzee adenovirus vector proposed in this study (chimpanzee adenovirus Oxford 1; ChAdOx1), a serogroup E adenovirus, has been administered to over 300 participants in trials of Middle East Respiratory Syndrome (MERS), influenza, TB, chikungunya, and prostate cancer, and has been safe and immunogenic. It has also been modified to enhance immunogenicity through the addition of a short shark invariant chain sequence and use of the tissue plasminogen promoter.

Hepatitis B virus circulates in the world as a number of genotypes (A-I), of which the most prevalent (especially in Asia) is genotype C [23]. The proteins expressed by ChAdOx1 in this study include most of the HBV genome from a genotype C consensus, including HBsAg, polymerase and core. In vitro experiments have demonstrated that the HBV polymerase was successfully inactivated through the insertion of point mutations at critical sites. In order to stop aggregation of surface antigen, this protein was split into two separate coding regions in the viral vectors.

The genetic HBV insert was then cloned into both the ChAdOx1 (chimpanzee adenovirus vectored hepatitis B virus vaccine; ChAdOx1-HBV) and the modified vaccinia virus Ankara (MVA; MVA-HBV) vectors.

This study is designed to assess the safety and immunogenicity of ChAdOx1-HBV and MVA-HBV, given either alone or with low doses of an anti-programmed cell death protein 1 (anti-PD-1) compound (nivolumab), and to assess the breadth of responses to the proteins encoded by these combinations. The T cell cross-reactivity to other genotypes will also be assessed. Doses of ChAdOx1 vaccines in previous studies have varied from 10^8 to over 5 x 10^10 viral particles (vp) per dose and a dose of 2.5 x 10^10 vp will be evaluated in this study to prepare for a further ChAdOx1/MVA heterologous prime-boost regimen. The dose of MVA of 1 x 10^8 pfu has been assessed safely in thousands of participants.

### **1.3 Summary of Non-clinical Studies**

Immunogen design: 1,447 HBV genotype C nucleotide sequences (HBV database) were aligned, and an HBV genotype C consensus sequence was generated. Then, a patient's HBV genotype C sequence (accession number: KP017269.1 HBV isolate JP-02) that had maximum similarity to the consensus was chosen for use in the HBV immunogen design. The HBV immunogen encompasses three full length HBV-antigens (pre-core/core, polymerase and preS1/preS2/surface) along with truncated shark invariant chain and tissue plasminogen activator genetic adjuvants and is encoded in the chimpanzee adenoviral vector. Point mutations were introduced within the polymerase protein encoded in the immunogen in order to abolish its function and to ensure no replication-competent HBV genome could arise from the immunogen sequences. An HBV-polymerase assay performed by the laboratory of [name] at University Hospital Freiburg, Germany, confirmed the absence of

polymerase activity of the polymerase contained in the HBV immunogen. A schematic of the HBV immunogen in both ChAdOx1 and in MVA is shown in [Figure 1](#).

**Figure 1 Schematic of Hepatitis B Virus Immunogens**

**A. ChAdOx1 insert**

**B. MVA insert**

The HBV immunogen was cloned and recovered into the ChAdOx1 vector genome to generate ChAdOx1-HBV and into MVA to generate MVA-HBV. Research stocks of the ChAdOx1-HBV vector were generated at the viral vector core facility of the Jenner Institute, University of Oxford.

Preclinical immunogenicity testing: ChAdOx1-HBV followed by MVA-HBV was found to be highly immunogenic when tested in mouse immunogenicity experiments in both inbred (C57BL/6) and outbred (CD-1) mice, measured using interferon-gamma (IFN- $\gamma$ ) enzyme-linked immunospot (ELISPOT) and intracellular cytokine staining assays. Excellent T cell responses were also observed to core, polymerase and surface HBV antigens in HLA-A2 transgenic mice receiving the prime-boost regimen.

A Good Laboratory Practice toxicology study of ChAdOx1-HBV and a separate Good Laboratory Practice toxicology study of MVA-HBV were conducted at Covance (UK), and showed minimal toxicity other than expected local site effects (see Investigator's Brochures for further study details and results).

#### **1.4 Summary of Clinical Experience**

One clinical study (HBV001) to investigate reactogenicity and explore the safety of ChAdOx1-HBV in healthy and CHB participants is ongoing at doses of  $2.5 \times 10^9$  and  $2.5 \times 10^{10}$  vp. At the higher dose, only localised swelling at the vaccination site and minor adverse events, which all resolved quickly, have been reported. There have been no reports of severe or serious adverse events (SAEs) or other safety concerns. There have been a large number of clinical studies using recombinant replication-incompetent adenoviruses followed by MVA to address a variety of diseases, such as HIV, HCV, TB, malaria, influenza and prostate cancer [24]. ChAdOx1 has been administered to over 300 participants (chikungunya, MERS, malaria, influenza and prostate cancer) and as the prime for an MVA boost in the malaria, influenza, tuberculosis and prostate cancer studies (NCT03203421, NCT01818362, NCT01623518, NCT01829490, NCT03815942 and NCT02390063). In all of those studies, extremely high levels of transgene-specific CD4+ and CD8+ T cells have been induced and there have been no vaccine-associated SAEs or evidence of autoimmunity. This is the first clinical study for the combination of the ChAdOx1-HBV and MVA-HBV vaccines.

Further information on ChAdOx1-HBV and MVA-HBV are contained in the respective Investigator's Brochures; these should be reviewed prior to study initiation.

## 1.5 Study Rationale

Chronic hepatitis B virus infection is a global public health challenge on the same scale as HIV and malaria. The current prophylactic vaccine has no effect on established chronic infection. Available treatments suppress viral replication, but they are not curative, largely due to the persistence of the viral covalently closed circular DNA (cccDNA), a transcriptional template in infected hepatocytes. Chronically infected patients fail to mount a cellular immune response that is sufficiently robust, functional, and sustained to clear the infection. Thus, in most cases, treatment must continue for life. However, even successfully virally suppressed patients may still develop liver cancer.

Many research programs are ongoing to develop new treatment concepts that focus on the clearance of HBsAg in a significant proportion of patients, with the principle aims of: 1) stopping treatment with no risk of relapse and no risk of liver disease progression and 2) to further decrease the risk of HCC.

Pre-clinical models still have considerable limitations in this indication, and important gaps in our understanding of the HBV replication cycle and the host immune response must be addressed to expand the exploitable vulnerabilities in the replication cycle that can be targeted therapeutically to cure the infection. A major effort has been made to compare the efficient integrated response resulting in HBV clearance of acute infection to the dysregulated response observed in patients with chronic hepatitis B. A complex interplay of innate and adaptive immune responses is essential for viral clearance and a failure of these responses can result in liver pathogenesis. CD8+ T cells are the main effector cells that eliminate the virus by cytolytic and non-cytolytic effector functions [25,26]. Sufficient CD4 T cell activity and the production of neutralising anti-HBV envelope antibodies may also be required for protective immunity [27].

Vaccitech is developing a prime boost vaccination strategy using two non-replicating viral vectors to deliver immunogens in various indications: ChAdOx1 followed by boosting with a heterologous vector, MVA, containing the same immunogen. These vectors are used to generate high magnitude CD4+ and CD8+ T-cell responses and also generate lasting cell-mediated immunity.

Adenoviral vectors represent exceptional priming vaccines but are difficult to reuse in the first few months after administration due to initial anti-vector immunity. For this reason, vaccine developers often use a different vector (known as a heterologous prime-boost) to augment the levels of the induced T cells [28,15].

MVA boosts and prolongs the CD4+ and CD8+ T cells induced by ChAdOx1. This two-dose heterologous vaccine regimen has been safe and immunogenic. ChAdOx1 and MVA including doses up to  $5 \times 10^{10}$  vp with ChAdOx1 and doses up to  $2.5 \times 10^8$  plaque forming units (pfu) with MVA were evaluated in various indications.

Chronic hepatitis B infection is also associated with upregulation of the PD-1/ programmed death-ligand 1 (PDL-1) inhibitor axis [29-32], and the use of checkpoint inhibitors has shown a therapeutic effect in some animal models [33]. Nivolumab and pembrolizumab have been administered to hundreds of hepatocellular carcinoma patients, many of whom were infected with hepatitis B, with no increase in liver toxicity and some effect on HBsAg reduction. In addition, a study of nivolumab, used at one tenth the licensed dose for oncology, combined with a partially immunogenic HBV vaccine was shown to be safe and to induce some HBsAg reduction [34]. The dose used was selected based on receptor occupancy studies which showed near maximal peripheral T cell receptor occupancy at 0.3 mg/kg. Further studies of anti-PD-1 and anti-PDL1 in chronic hepatitis B are underway.

Studies examining the effect of checkpoint inhibitors and many other interventions have focused on patients with low levels of serum hepatitis B DNA and levels of HBsAg measured at  $< 10^4$  IU/mL, and in patients who have well controlled CHB while on antiviral agents, which at present is dominated by the use of tenofovir (or its prodrug, tenofovir alafenamide fumarate) or entecavir. Most functional cures either on therapy or at therapy discontinuation have been observed in such patients.

Thus, a prime-boost strategy using ChAdOx1 vector (ChAdOx1-HBV) and an MVA vector (MVA-HBV), with and without nivolumab will be evaluated in this study. In order to decrease potential safety issues, only participants with stable antiviral therapy in the previous one year with resultant low HBV DNA and HBsAg will be enrolled. As the T cell responses may wane with time, and a boost to the highest levels may be needed to sustain an ongoing response (as evidenced by some lowering of the HBsAg levels), a boost using the MVA vaccine is permitted at Month 3, at the discretion of the Investigator and concurrence of the Sponsor (UK participants only).

Comprehensive reviews of ChAdOx1-HBV and MVA-HBV are contained in the respective Investigator's Brochures; these and the Package Insert for nivolumab should be reviewed prior to study initiation.

## 2 STUDY OBJECTIVES AND ENDPOINTS

### Objectives

### Endpoints

#### Primary Objectives

- Determine the safety and reactogenicity of the following in participants with CHB infection and virally suppressed with oral antiviral medication:
  - MVA-HBV vaccine
  - ChAdOx1-HBV plus MVA vaccines
  - ChAdOx1-HBV plus MVA vaccines and nivolumab

#### Primary Endpoints

- Safety and reactogenicity of the vaccine(s): incidence of adverse events, SAEs,  $\geq$ Grade 3 study vaccine-related adverse events within 4 weeks of vaccination
- Safety of the vaccines with nivolumab: incidence of adverse events, SAEs,  $\geq$ Grade 3 adverse events within 4 weeks of dosing
- Incidence of adverse events of special interest (AESIs)
- Number and proportion of participants reporting treatment-emergent adverse events within each treatment group
- Number and proportion of participants within each treatment group with potentially clinically significant laboratory values and vital signs within each treatment group
- Change from baseline in laboratory tests and vital sign measurements to each time point of collection

#### Secondary Objectives

- Determine the immunogenicity of the following in participants with CHB infection and virally suppressed with oral antiviral medication:
  - MVA-HBV vaccine
  - ChAdOx1-HBV plus MVA-HBV vaccines
  - ChAdOx1-HBV plus MVA-HBV vaccine administered with nivolumab
- Determine the impact of PD-1 blockade timing relative to vaccination on immunogenicity in participants with CHB infection and virally suppressed with oral antiviral medication
- Determine the effect of C the following on the level of hepatitis B markers:
  - ChAdOx1-HBV plus MVA-HBV vaccines without nivolumab

#### Secondary Endpoints

- Magnitude and avidity of HBV specific CD4 + and CD8+ T cells induced by each regimen
- Effect on the frequency and magnitude of HBV infection markers (HBsAg, Hepatitis B surface antibody [HBsAb] seroconversion, hepatitis B DNA, HBeAg)

- ChAdOx1-HBV plus MVA-HBV vaccines with nivolumab

#### Exploratory Objectives

- Assess the HBV specific cellular immune response generated by ChAdOx1-HBV plus MVA-HBV vaccines
- Determine the effect of ChAdOx1-HBV plus MVA-HBV on hepatitis B biomarkers

#### Exploratory Endpoints

Exploratory endpoints may include, but may not be limited to:

- Effect on hepatitis B core-related Ag (HBcrAg)
- Effect on hepatitis B pregenomic RNA (HBpgRNA)
- Induction of individual phenotypic subsets of CD4+ and CD8+ T cells induced by vaccination
- The T cell breadth of response to the HBV proteins encoded by the ChAdOx1-HBV plus MVA-HBV vaccines
- Frequency of regulatory T cells responses

[figure not shown]
### 3 STUDY OVERVIEW

#### 3.1 Overall Study Design and Methodology

##### 3.1.1 Study Overview

This is a Phase 1b/2a, multicentre study of ChAdOx1-HBV and MVA-HBV vaccines (VTP-300). The study is planned to be conducted at up to 15 centres in up to approximately 52 participants chronically infected with Hepatitis B Infection and virally suppressed with approved oral anti-HBV therapies. This is an open-label study comparing the safety, tolerability and immunogenicity of MVA-HBV alone, ChAdOx1-HBV followed by MVA-HBV, and ChAdOx1-HBV plus MVA vaccine with the anti-PD-1 antibody, nivolumab. The study design is shown in Figure 2. Version 6.0 of the study protocol has closed Groups 1 and 4 to further randomisation; recruitment will now be in a 1:1 ratio between Groups 2 and 3 only. This is due to the fact that significant decreases in surface antigen were seen in Group 3 at month 3, and that 2/6 Group 2 patients also had a greater than 0.5 log decrease at that time point.

**Figure 2 Overall Study Design**

Abbreviations: ChAdOx1=chimpanzee adenovirus vector; HBV=hepatitis B virus; MVA=modified vaccinia virus Ankara; pfu=plaque forming units; vp=viral particles

Greyed Groups = closed

All treatment groups will receive study vaccine on Day 0 and Day 28. In Group 1, MVA-HBV will be evaluated 7 days after the first dose of study vaccine in the first 6 participants prior to initiation of the prime-boost regimen of ChAdOx1-HBV followed by MVA-HBV (Group 2). Participants in Groups 3 and 4 will be dosed in parallel to receive ChAdOx1-HBV (with and without nivolumab) on Day 0 followed by MVA-HBV with nivolumab on Day 28. Groups 3 and 4 will be initiated after evaluation of data 7 days after the first 6 participants in Group 2 have received ChAdOx1-HBV. The evaluations will be carried out by a Safety Monitoring Committee (SMC) consisting of the Sponsor Medical Monitor, the Country Lead Investigators for South Korea, Taiwan and the UK, and the trial Medical Monitor. If a participant has a 0.5 log or greater drop in hepatitis B surface antigen at Day 35, they may receive a booster dose of MVA-HBV, at the Investigator's discretion and after discussion with the Sponsor (UK participants only).

A Data Monitoring Committee (DMC) composed of three independent experts (two clinicians and one statistician) will be appointed to perform unscheduled reviews of the available safety and tolerability study data and make recommendations concerning the continuation, modification or termination of the study if one of the study stopping or holding rules defined in [Section 3.1.3](#) is met.

### ***3.1.2 Duration of Study***

#### ***3.1.2.1 Duration for each Participant***

Up to 10.5 months (up to 1.5 months for screening and 9 months on the study with study vaccine given on Day 0).

#### ***3.1.2.2 Duration of Whole Study***

It is planned that the study will take 17 months to implement, enrol and read out.

The end of the study is defined as the date of database lock.

### ***3.1.3 Stopping Criteria/Holding Criteria***

There will be a review of the study data by the DMC when there is a reasonable possibility that the investigational vaccine caused any of the SAEs or severe adverse events listed below, based on the assessment of the Investigator, in one or more participants at any dose. Vaccinations will be put on hold pending this review:

- Death related to study vaccine
- Life-threatening adverse event or life-threatening suspected reaction
- Serious suspected adverse reaction
- Suspected unexpected serious adverse reaction (SUSAR)
- Acute allergic reaction or anaphylactic shock following the administration of vaccine investigational product
- Anaphylaxis or bronchospasm, indicative of an immediate hypersensitivity reaction to study vaccine
- If any participant has any of the following during the study:
  - Alanine aminotransferase (ALT) or aspartate aminotransferase (AST) >3 x upper limit of normal (ULN) and total bilirubin >2 x ULN or International Normalised Ratio (INR) >1.5
  - ALT or AST >3 x ULN with the appearance of fatigue, nausea, vomiting, right upper quadrant pain or tenderness, fever, rash, and/or eosinophilia (>5%)
  - Grade 4 diarrhoea, hypothyroidism, hyperthyroidism, hypophysitis, adrenal insufficiency, rash, toxic epidermal necrolysis, Stevens-Johnson syndrome, diabetes, other immune-related adverse reaction, or creatinine elevation
  - Grade 3 myocarditis or pneumonitis
  - Solicited local adverse events: If three out of the first 20 participants dosed with a study vaccine, or >10% of participants, thereafter, are followed by the same Grade 3 solicited local adverse event

- Solicited systemic adverse events: If three out of the first 20 participants dosed with a study vaccine, or >10% of participants, thereafter, are followed by the same Grade 3 solicited systemic adverse event
- Unsolicited adverse events: If three participants of the first 20 participants dosed, or >10% of participants, thereafter, develop a Grade 3 unsolicited adverse event of the same type that is considered related to study vaccine

Other potential reasons for discontinuation of the second planned dose of nivolumab for Group 4 are found in [Appendix 2 – Toxicity Management Guidelines for Nivolumab](#).

If, following review of data, a recommendation is made by the DMC to resume study enrolment and vaccine administration, the DMC will record their judgment in a memorandum to the study file and notify the Sponsor. The DMC memorandum will be forwarded to the local Medical Monitor and Investigators and an appropriate substantial amendment filed.

If the study is terminated early, the Regulatory Authorities, IEC/IRBs and study centres will be notified within 15 days according to local requirements.

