### ***8.1.5 Data Monitoring Committee***

A DMC, composed of three independent experts (two clinicians and one statistician), will be appointed to review the study data and make recommendations concerning the continuation, modification, or termination of the study. The DMC will perform the following:

- Evaluation of study conduct and progress and review of the cumulative safety and efficacy data. Meetings will take place as follows:
  - Kick off meeting before the first participant is enrolled
  - Perform unscheduled review of data if one of the study stopping or holding rules is met, see Section 3.1.3.
  - Meet if requested by the SMC

The DMC will operate in accordance with the study-specific DMC Charter, which will be agreed prior to the start of enrolment.

The chair of the DMC may be contacted for advice and independent review by the Investigator or Sponsor in any other situation where the Investigator or Sponsor feels independent advice or review is important.

The DMC will also be notified within 24 hours of the Investigators' being aware of any study vaccine-related SAEs. The DMC has the power to place the study on hold if deemed necessary.

Following review of data by the DMC, a recommendation to resume, modify or halt study enrolment and vaccine administration will be made, and the DMC will record their judgment in a memorandum to the study file and notify the Sponsor. In the event of halting or modification of the protocol, the DMC memorandum will be forwarded to the local Medical Monitor and Investigators.

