#### 8.2.1.2 Adverse Reaction

An adverse reaction is defined as any untoward and unintended response to study vaccine related to any dose administered.

An unexpected adverse reaction is an adverse reaction in which the nature or severity of which is not consistent with the Investigator's Brochure or Prescribing Information.

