#### *8.2.1.4 Suspected Unexpected Serious Adverse Reaction*

A SUSAR is any suspected adverse reaction related to the study vaccine that is both unexpected and serious.

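### Protocol 3.1.3 ties the mandatory DMC review and hold to the vaccine: a death or serious reaction attributed to nivolumab alone does not meet the death or serious-reaction items, and the liver and immune items are ambiguous.

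*Protocol*

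**What the plan says.** Protocol 3.1.3 opens with one condition. The DMC reviews the data, and vaccinations are held meanwhile, "when there is a reasonable possibility that the investigational vaccine caused any of the SAEs or severe adverse events listed below". The investigator makes that judgement, and one participant is enough.

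The list that follows includes deaths (limited to vaccine-related ones), life-threatening events, serious suspected adverse reactions, SUSARs and allergic reactions. It also has a sub-list of liver and immune-type events, headed "If any participant has any of the following during the study". The section closes by pointing to Appendix 2 for "Other potential reasons for discontinuation of the second planned dose of nivolumab for Group 4".

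Two of the listed terms are defined elsewhere. Section 8.2.1.2 defines an adverse reaction as "any untoward and unintended response to study vaccine related to any dose administered". Section 8.2.1.4 says "A SUSAR is any suspected adverse reaction related to the study vaccine that is both unexpected and serious". The causality question in 8.2.4.2 asks only about the study vaccine.

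Section 8.1.5 has the DMC meet at kick-off, at the SMC's request, or to "Perform unscheduled review of data if one of the study stopping or holding rules is met". Its 24-hour notice to the DMC runs from investigators "being aware of any study vaccine-related SAEs".

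**The concern.** Nivolumab is listed as an investigational product (5.1.2), with its own expectedness reference (8.2.5.3) and its own causality assessment (SAP 10.5.2). The primary endpoint for vaccines given with nivolumab is not restricted to vaccine-related events (Protocol 2), and the DMC outputs include nivolumab-related events of Grade 3 or above (SAP 16.0). The rule that obliges the DMC to look is the part that leaves nivolumab out.

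This matters most for Group 3, the only nivolumab group still open in Version 6.0. Its participants receive one nivolumab dose, on Day 28. The withhold-or-discontinue rules in Appendix 2 therefore have no later nivolumab dose to act on in the affected participant. What an event in one participant can still change is whether others go on to be dosed, and the mandatory instrument for that is the study-wide hold.

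**Working it through.** The point is textual. The main 3.1.3 items are tested below against an event that the investigator attributes to nivolumab and not to the vaccine. The two readings are that the lead-in governs every item, or that each item stands on its own words. Solicited-event counts are left out because they concern vaccine reactogenicity.

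| 3.1.3 item | Relation term of its own | Met if lead-in governs? | Met if item stands alone? |
|---|---|---|---|
| Death | Study vaccine, stated in the item | No | No |
| Serious suspected adverse reaction | Study vaccine, through 8.2.1.2 | No | No |
| SUSAR | Study vaccine, through 8.2.1.4 | No | No |
| Grade 3 unsolicited events of one type | Study vaccine, stated in the item | No | No |
| Allergic reaction; anaphylaxis or bronchospasm | First tied to vaccine administration in time, second to the vaccine as cause | No | First arguably, second no |
| Life-threatening event | None for the event itself | No | Yes |
| Liver and immune sub-list | None in the header | No | Yes |

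The first four rows fail on both readings. The last two depend on the reading. A fatal event attributed to nivolumab alone could still be caught if it also met one of those two items read as stand-alone, such as Grade 3 myocarditis.

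Other routes to a review or hold:

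- DMC unscheduled review (8.1.5) refers back to 3.1.3, so it adds no trigger.
- The 24-hour SAE notice (8.1.5) is limited to vaccine-related events in its own words. The SUSAR notice in 8.2.5 is limited through the definitions.
- AESIs (8.3) go to the sponsor whatever the attribution, with no hold or DMC review stated.
- The SMC must evaluate ALT or AST above 10 x ULN, or above 5 x ULN for more than 3 weeks, whatever the attribution (8.1.4). Referral to the DMC is at its discretion.
- Appendix 2 acts only on the affected participant's own nivolumab dosing.

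None of these makes a DMC review or hold mandatory for an event attributed to nivolumab alone.

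Scope, from Protocol 3.2 and SAP 8.1:

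- Group 3 planned 16, in the Month 3 review 6: 16 - 6 = 10 outside that review.
- Group 4 closed at 9. Assuming Group 3 had reached the same size, because the two opened together with equal allocation: 16 - 9 = 7.
- Follow-up after Group 3 nivolumab (SAP Table 3): 273 - 28 = 245 days. The 28-day AE window ends on Day 28 + 27 = Day 55, leaving 273 - 55 = 218 days. This is one participant's follow-up, not the time during which others await dosing.

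No event rate can be derived. Protocol 3.3 reports no immune-related events in published data at 0.3 mg/kg but gives no denominator.

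**The case against.** The strongest reply is that the liver and immune items have their own header, "If any participant has any of the following during the study", with no causality term, while other items carry one. If the lead-in governed everything, those separate qualifiers would be largely redundant. The closing sentence, on "Other potential reasons for discontinuation of the second planned dose of nivolumab for Group 4", reads as though the list already covers nivolumab, and the immune items closely track the permanent-discontinuation rows of Appendix 2. This stands as evidence of intent. A reader might infer that every listed immune event attributed to nivolumab is excluded from the rule; the documents do not support that. They leave it unclear, because the items are still listed under the lead-in. The reply does not reach the death, serious-reaction and SUSAR items.

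Second, attribution to nivolumab alone should be uncommon. The infusion follows vaccination on the same day (5.8.2.3), and under 8.2.4.2 a reasonable possibility that the vaccine contributed is enough. This stands. What remains is mainly late events, which Appendix 2 says can appear months after the last dose.

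Third, others can act. All SAEs and AESIs reach the sponsor. The SMC reviews data throughout and can ask the DMC to meet, and the investigator or sponsor may consult the DMC chair. The local Medical Monitor may suspend enrolment (8.2.5), and "The DMC has the power to place the study on hold if deemed necessary". The investigator may also pause the study, though 8.1.1 words that for the vaccine. So it would be wrong to infer that nivolumab recipients had no protection. These powers are discretionary, however, and 3.1.3 exists to remove discretion.

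Fourth, a vaccination hold already stops nivolumab, because nivolumab is given only after vaccination (5.2.2, 5.8.2.3). This is correct and simplifies the fix.

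**Conclusion.** The point holds in a limited form. For death, serious suspected adverse reaction and SUSAR, a nivolumab-only attribution does not meet the item on any reading. For the liver and immune sub-list the text is ambiguous, with stand-alone triggers the likelier intent. No other mandatory route to a DMC review or hold closes the gap.

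The 7 to 10 planned Group 3 participants are a ceiling on who could have benefited from a hold at Version 6.0. The lower figure rests on the assumption that Group 3 matched Group 4 at closure. Later events leave fewer people undosed, while replacements (4.1, 5.7) could add a few. The figure should not be read as a number harmed or expected to be harmed. No efficacy estimate is affected. The DMC Charter and Safety Management Plan were not available and may contain further triggers.

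**What to change.** If dosing continues, one protocol amendment should make these edits:

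1. In the 3.1.3 lead-in, replace the reference to the vaccine with *the study vaccine and/or nivolumab*, and extend the death item to deaths related to either product. In the same edit, state whether the liver and immune sub-list applies regardless of attribution. Its header suggests it does, and without that statement the new lead-in could narrow it.
2. Extend the definitions in 8.2.1.2 and 8.2.1.4, and the 24-hour DMC notice in 8.1.5, to nivolumab-related events.
3. In 8.2.4.2, ask the causality question separately for study vaccine and nivolumab, matching SAP 10.5.2.

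Adding nivolumab dosing to the wording of the hold is optional. The cost is wording in five sections and a possible extra temporary hold, with a substantial amendment needed to resume (3.1.3). Outside the sub-list, the causality condition stays, so clearly unrelated events do not stop the study through those items.

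Dosing may well be complete: the SAP 1.2 entry in the change history (December 2022) records that no participant had the Month 3 boost. In that case, list in the study report the Group 3 and 4 events that met a 3.1.3 item, with attribution to each product and whether a review or hold followed. The narratives and AE listings already planned hold most of the detail. No new data are needed if relationship to nivolumab was recorded as SAP 10.5.2 describes.
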